### 6.6.2 Day 40 to Day 89 (Follow-Up Safety Visit)

For subjects who remain hospitalized between Day 40 and Day 90 at the institution where they receive study treatment, a follow-up safety visit will be performed on the day of discharge.

The following procedures will occur on the day of hospital discharge for subjects who are discharged between Day 40 and Day 90:

- Perform limited physical examination (to include, at a minimum, a pulmonary examination [including auscultation]);
- Obtain vital sign measurements, including oxygenation status;
- Assess ventilator device status (if applicable);
- Obtain a blood sample for ADAs;
- Perform 12-lead ECG;
- Assess for survival and discharge disposition;
- Obtain a blood sample for PK measurement and assessment of anti-*S. aureus* toxin antibodies;
- Track days on ventilator from randomization (if applicable);
- Track days in ICU (or other observation area) from randomization;
- Record concomitant medications; and
- Perform adverse event assessment.

### 6.6.3 Safety Visit (Day 90 [ $\pm 7$ Days])

The following procedures will be performed at the Safety Visit on Day 90 ( $\pm 7$  days). If the subject is unable to return to the site, this visit may be conducted by telephone, with procedures performed as appropriate (i.e., concomitant medications and adverse events collected):

- Perform limited physical examination (to include, at a minimum, a pulmonary examination [including auscultation]);
- Obtain vital sign measurements, including oxygenation status;

- Assess ventilator device status (if applicable);
- Obtain a blood sample for ADAs;
- Perform 12-lead ECG;
- Assess for survival and discharge disposition;
- Obtain a blood sample for PK measurement and assessment of anti-*S. aureus* toxin antibodies;
- Track days on ventilator from randomization;
- Track days in ICU (or other observation area) from randomization;
- Record concomitant medications; and
- Perform adverse event assessment.

### **6.7 Early Termination Visit and Withdrawal Procedures**

For subjects who are withdrawn from the study prior to Day 22, the following procedures will be performed at an Early Termination Visit:

- Perform limited physical examination (to include, at a minimum, a pulmonary examination [including auscultation]);
- Obtain vital sign measurements, including oxygenation status;
- Perform pregnancy test for female subjects of childbearing potential only;
- Perform clinical laboratory assessments including chemistry, hematology, coagulation, and urinalysis (if clinically indicated);
- Obtain a blood sample for procalcitonin testing;
- Assess ventilator device status (if applicable);
- Obtain adequate respiratory specimen for culture (if clinically indicated);
- Assess for clinical signs/symptoms of pneumonia (Section 7.4.2; Table 1);
- Assess for other *S. aureus*-associated infections;
- Obtain a blood sample for ADAs;
- Perform 12-lead ECG;
- Assess for survival and discharge disposition;
- Obtain a blood sample for PK measurement and assessment of anti-*S. aureus* toxin antibodies;
- Track days on ventilator from randomization;
- Track days in ICU (or other observation area) from randomization;
- Record concomitant medications; and
- Perform adverse event assessment.

## 7 EFFICACY ASSESSMENTS

### 7.1 Primary Efficacy Endpoint

The primary efficacy endpoint is the proportion of subjects in the MITT Population who develop *S. aureus* pneumonia as defined in Section 7.4 up to but not including Day 22.

### 7.2 Secondary Efficacy Endpoints

The secondary efficacy endpoints include:

- Duration of mechanical ventilation during the first 21 days post-randomization for subjects in the MITT, Intent-to-Treat (ITT), and Per Protocol (PP) Populations;
- Length of ICU stay during the first 21 days post-randomization for subjects in the MITT, ITT, and PP Populations;
- The  $C_{max}$ ,  $T_{max}$ , AUC, and  $t_{1/2}$  of ASN-1 and ASN-2 in serum following a single dose of ASN100 in the PK Population; and
- 28-day all-cause mortality in the MITT, ITT, and PP Populations.

### 7.3 Exploratory Efficacy Endpoints

Exploratory efficacy endpoints include:

- Proportion of subjects in the MITT and PP Populations with a diagnosis of HABP at >48 hours post-extubation up to but not including Day 22 in extubated subjects;
- Proportion of subjects in the MITT and PP Populations with development of VABP up to but not including Day 22;
- Incidence of all bacterial pneumonias in the MITT, ITT, and PP Populations;
- Incidence of other non-*S. aureus* pneumonias up to but not including Day 22 in the MITT, ITT, and PP Populations; and
- Incidence of other *S. aureus* infections acquired following study drug administration up to but not including Day 22 in the MITT, ITT, and PP Populations.

## 7.4 Microbiological and Clinical Assessments

### 7.4.1 Microbiological Assessment

ETA specimens will be collected for culture during Screening/Enrollment to determine the degree of *S. aureus* colonization. Additional respiratory specimens may be collected for culture throughout the Monitoring Period or Early Termination (if applicable) if clinically indicated according to standard of care.

If, as part of routine standard of care, additional respiratory and/or other microbiological specimens are collected for culture during the study, results will be documented within the eCRF. As fully described within the study lab manual, bacterial isolates recovered from these specimens that are deemed pathogens by the Investigator (if retained and available at the study site local microbiology laboratory) will be sent to a central microbiology laboratory for confirmation of pathogen identification (all isolates) and susceptibility testing (*S. aureus* isolates only).

During the Monitoring Period, a diagnosis of *S. aureus* pneumonia will be determined if subjects have *S. aureus* identified from an adequate respiratory specimen (Section 7.4.1) and clinical signs and symptoms of pneumonia. For a diagnosis of *S. aureus* pneumonia, clinical signs and symptoms must occur  $\pm 2$  days from the time of collection of an adequate respiratory specimen culture that is positive for *S. aureus* (Section 7.4.2).

- For intubated subjects, a respiratory specimen obtained by BAL, non-bronchoscopic BAL, or protected specimen brush will be considered an adequate respiratory specimen; or
- For extubated subjects, an adequate expectorated/induced sputum specimen is defined as  $<10$  squamous epithelial cells and  $>25$  PMNs/100 $\times$  field; and
- For both intubated and extubated subjects, adequate respiratory specimens will undergo either semi-quantitative or quantitative culture in accordance with the local laboratory's standard procedure.

### 7.4.2 Assessment of Clinical Signs and Symptoms

Subjects will be assessed daily throughout the Monitoring Period for the following clinical signs and symptoms presented in Table 1.

**Table 1. Clinical Signs and Symptoms**

Mechanically Ventilated Subjects	Non-Mechanically Ventilated Subjects

 
• Cough,
 
• Rales,
 
• Dullness on percussion,*
 
• Bronchial breath sounds,
 
• Egophony,*
 
• Need for suctioning,
 
• Need for ventilator support, and
 
• Fever <math>\geq 38^{\circ}\text{C}</math> (<math>\geq 100.4^{\circ}\text{F}</math>).
 
	
 
• Cough,
 
• Rales,
 
• Dullness on percussion,*
 
• Bronchial breath sounds,
 
• Egophony,*
 
• Dyspnea,
 
• Tachypnea,
 
• Respiratory rate,
 
• Hypoxemia, and
 
• Fever <math>\geq 38^{\circ}\text{C}</math> (<math>\geq 100.4^{\circ}\text{F}</math>).
 

*If routinely performed.	

A diagnosis of pneumonia (HABP or VABP) will be determined as defined in Table 2.

**Table 2. Definition of Hospital-Acquired and Ventilator-Associated Bacterial Pneumonia**

Indication	Definition
HABP	
 
• A chest X-ray showing new or progressive infiltrates suggestive of pneumonia (as assessed by the Investigator);
 
• At least ONE of the following:               
 
○ Has been hospitalized for >48 hours, or
 
○ Developed clinical signs and symptoms within 7 days following hospital discharge;
 
 
 
• At least ONE of the following:               
 
○ New onset or worsening pulmonary signs/symptoms such as cough, dyspnea, tachypnea (e.g., respiratory rate >25 breaths per minute), expectorated sputum production, or the requirement for mechanical ventilation (if subject is not already ventilated);
 
○ Need for acute changes in ventilator support to enhance oxygenation or to the amount of PEEP; or
 
○ New onset of suctioned respiratory secretions; AND
 
 
 
• At least ONE of the following clinical signs/symptoms:               
 
○ Temperature >38°C or <35°C,
 
○ WBC count ≥10,000 cell/mm^3 or ≤4500 cell/mm^3, or
 
○ >15% immature neutrophils (bands) on peripheral blood smear.
 
 
 

VABP	
 
• A chest X-ray showing new or progressive infiltrates suggestive of pneumonia (as assessed by the Investigator);
 
• Subject has received mechanical ventilation via an endotracheal or nasotracheal tube for ≥48 hours;
 
• At least ONE of the following:               
 
○ New onset or worsening pulmonary signs/symptoms such as cough, dyspnea, tachypnea (e.g., respiratory rate >25 breaths per minute), expectorated sputum production, or the requirement for mechanical ventilation (if subject is not already ventilated);
 
○ Need for acute changes in ventilator support to enhance oxygenation or to the amount of PEEP; or
 
○ New onset of suctioned respiratory secretions; AND
 
 
 
• At least ONE of the following clinical signs/symptoms:               
 
○ Temperature >38°C or <35°C,
 
○ WBC count ≥10,000 cell/mm^3 or ≤4500 cell/mm^3, or
 
○ >15% immature neutrophils (bands) on peripheral blood smear.
 
 
 

HABP = hospital-acquired bacterial pneumonia; PEEP = positive end-expiratory pressure; VABP = ventilator-associated bacterial pneumonia; WBC = white blood cell.
	

## 8 PHARMACOKINETIC ASSESSMENTS

### 8.1 Pharmacokinetic Endpoint

The primary PK endpoints are the  $C_{max}$ ,  $T_{max}$ , AUC, and  $t_{1/2}$  of ASN-1 and ASN-2 in serum following a single IV dose of ASN100 in the PK Population.

The levels of ASN-1 and ASN-2 will be measured in BAL fluid in a PK sub-study which will allow the calculation of a blood to ELF ratio.

### 8.2 Pharmacokinetic Assessments

Samples for PK analysis will be obtained to determine the PK of ASN-1 and ASN-2 in serum and BAL fluid (for subjects participating in the BAL fluid PK sub-study only). Instructions for the collection, handling, and storage of biological samples will be provided in a separate Laboratory Manual.

In order to maintain the study blind, all subjects, including those randomized to receive placebo, will have PK samples obtained at the specified time points. The actual date and time of each sample will be recorded.

Drug concentration information that may unblind the study will not be reported to investigative sites or blinded Sponsor or CRO personnel until the study has been unblinded.

#### 8.2.1 Serum Pharmacokinetic Sampling

Blood samples will be obtained for the measurement of ASN-1 and ASN-2 in serum. At the completion of the second infusion, blood samples for PK analysis will be collected immediately following the completion of the second infusion (+15 minutes) and at 6 hours ( $\pm 4$  hours) and 24 hours ( $\pm 6$  hours) post-dose.

In addition, a PK sample will be obtained from all subjects on Days 4 ( $\pm 1$  day), 7 ( $\pm 1$  day), 14 ( $\pm 2$  days), and 22 ( $+2$  days) of the Monitoring Period. Additional PK samples will be collected on the day of discharge (if discharge occurs between Day 40 and Day 90), on Day 90 (if hospitalized or if the subject is able to return to the clinic), or Early Termination (if applicable).

The following serum PK parameters will be assessed:

- Maximum serum concentration ( $C_{max}$ ),
- Time to maximum serum concentration ( $T_{max}$ ),
- Area under the serum concentration-time curve (AUC), and
- Terminal elimination half-life ( $t_{1/2}$ ).

Subjects participating in the BAL fluid PK sub-study will have a blood sample collected for PK measurement  $\pm 1$  hour relative to BAL fluid collection (including scheduled BAL fluid collection or if BAL fluid is collected as part of a standard of care procedure from any subject enrolled in the sub-study at any time post-randomization).

### 8.2.2 Bronchoalveolar Lavage Fluid Pharmacokinetic Sampling

Select sites will be invited to participate in a BAL fluid PK sub-study. Approximately 25 to 35 subjects who volunteer will participate in this sub-study and will have BAL fluid collected 48 hours ( $\pm 36$  hours) post-dose (on approximately Day 2 or Day 3, depending on time of study drug administration) to determine ASN-1 and ASN-2 levels and blood to ELF ratio. If BAL fluid is collected as part of a standard of care procedure from any subject enrolled in the sub-study at any other time post-randomization for any other reason, if possible, a sample for PK analysis will also be obtained.

### 8.2.3 Analysis of Anti-*Staphylococcus aureus* Toxin Antibody Titers

Blood samples obtained for ADA and PK analysis purposes will also be used to assess the amount of pre-existing anti-*S. aureus* toxin antibodies and the toxin neutralizing titer of the serum sample prior to and after randomization. Only antigen-specific antibody titers will be determined and no genetic information will be extracted from these samples. Samples will be destroyed following the completion of all *S. aureus* anti-toxin antibody analyses.

## 9 SAFETY ASSESSMENTS

### 9.1 Adverse Events

An adverse event is defined as any untoward medical occurrence in a clinical investigation subject administered a pharmaceutical product, which does not necessarily have a causal relationship with this treatment. An adverse event can therefore be any unfavorable and/or unintended sign (including an abnormal laboratory finding), symptom, or disease temporally associated with the use of an investigational medicinal product, whether or not related to the investigational medicinal product. All adverse events, including observed or volunteered problems, complaints, or symptoms, are to be recorded on the appropriate eCRF.

Adverse events that occur between the time the subject signs the ICF and the Randomization Visit will only be recorded if related to a study-specific procedure. Beginning with randomization all adverse events, which include clinical laboratory test and physical examination variables, will be monitored and documented until study participation is complete. Subjects should be instructed to report any adverse event that they experience to the Investigator. Site personnel will ensure each adverse event is recorded on the appropriate adverse event eCRF.

Wherever possible, a specific disease or syndrome rather than individual associated signs and symptoms should be identified by the Investigator and recorded on the eCRF. However, if an observed or reported sign or symptom is not considered a component of a specific disease or syndrome by the Investigator, it should be recorded as a separate adverse event on the eCRF. Additionally, the condition that led to a medical or surgical procedure (e.g., surgery, endoscopy, tooth extraction, or transfusion) should be recorded as an adverse event, not the procedure.

Any medical condition already present at the time of randomization should not be reported as an adverse event unless the medical condition or signs or symptoms present at baseline change in severity or seriousness at any time during the study. In this case, it should be reported as an adverse event.

Clinically significant abnormal laboratory or other examination (e.g., ECG) findings that are detected during the study or are present at the time of randomization and significantly worsen during the study should be reported as adverse events. The Investigator will exercise his or her medical and scientific judgment in deciding whether an abnormal laboratory finding or other abnormal assessment is clinically significant. Clinically significant abnormal laboratory values occurring during the clinical study will be followed until repeat tests return to normal, stabilize, or are no longer clinically significant. Any abnormal test that is determined to be an error does not require reporting as an adverse event.

Lack of efficacy (i.e., development of pneumonia as defined in Section 7.4) will be captured as an efficacy measure and in general will not be considered an adverse event; however, new onset of specific pulmonary symptoms that do not meet the study-specific definition of pneumonia or worsening of baseline signs and symptoms should be captured as adverse events. Events that meet the criteria for an SAE (Section 9.2) should follow the procedures for SAE reporting as detailed in Section 9.3.

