## 9.2 Serious Adverse Events

An adverse event or adverse reaction is considered serious if, in the view of either the Investigator or Sponsor, it results in any of the following outcomes:

- Death;
- A life-threatening adverse event;
  - NOTE: An adverse event or adverse reaction is considered “life-threatening” if, in the view of either the Investigator or Sponsor, its occurrence places the subject at immediate risk of death. It does not include an event that, had it occurred in a more severe form, might have caused death.
- Requires hospitalization or prolongation of existing hospitalizations;
  - NOTE: Any hospital admission with at least 1 overnight stay will be considered an inpatient hospitalization. An emergency room visit without hospital admission will not be recorded as a SAE under this criterion, nor will hospitalization for a procedure scheduled or planned before signing of informed consent. However, unexpected complications and/or prolongation of hospitalization that occur during elective surgery should be recorded as adverse events and assessed for seriousness. Admission to the hospital for social or

situational reasons (i.e., no place to stay, live too far away to come for hospital visits) will not be considered inpatient hospitalizations.

- A persistent or significant disability/incapacity or substantial disruption of the ability to conduct normal life functions;
  - A congenital anomaly/birth defect; or
  - An important medical event.
- NOTE: Important medical events that may not result in death, be life-threatening, or require hospitalization may be considered an SAE when, based upon appropriate medical judgment, they may jeopardize the subject and may require medical or surgical intervention to prevent one of the outcomes listed above. Examples of such medical events include allergic bronchospasm requiring intensive treatment in an emergency room or at home, blood dyscrasias or convulsions that do not result in inpatient hospitalizations, or the development of drug dependency.

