### **9.3 Serious Adverse Event Reporting – Procedures for Investigators**

#### **Initial Reports**

Serious adverse events related to a study-specific procedure that occur between the Screening Visit and the Randomization Visit, and all SAEs occurring from the time of randomization until the Day 90 Safety Visit, must be reported to Medpace Clinical Safety within 24 hours of the knowledge of the occurrence (this refers to any adverse event that meets any of the aforementioned serious criteria). All SAEs that the Investigator considers related to study drug occurring after the Day 90 Safety Visit must be reported to the Sponsor.

To report the SAE, complete the SAE form electronically in the electronic data capture (EDC) system for the study. When the form is completed, Medpace Safety personnel will be notified electronically and will retrieve the form.

If the event meets serious criteria and it is not possible to access the EDC system, send an email to Medpace Safety at [[contact]](mailto:[contact]) or call the Medpace SAE hotline (phone number listed below), and fax the completed paper SAE form to Medpace (fax number listed below) within 24 hours of awareness. When the EDC system becomes available, the SAE information must be entered within 24 hours of the system becoming available.

Safety Contact Information: Medpace Clinical Safety

Medpace SAE hotline – USA:

[contact], Dial 3 or [contact], Dial 3

[contact] or [contact]

Email: [[contact]](mailto:[contact])

Medpace SAE hotline – Europe:

[contact]

[contact]

Email: [[contact]](mailto:[contact])

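### Protocol 9.1 exempts pneumonia from adverse-event recording without naming an organism or an end date, so non-serious, non-*S. aureus* pneumonia may be missing from the safety tables

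*Protocol*

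**What the plan says.** Protocol 9.1 sets the default: "Beginning with randomization all adverse events, which include clinical laboratory test and physical examination variables, will be monitored and documented until study participation is complete". It then makes an exception to adverse-event recording: "Lack of efficacy (i.e., development of pneumonia as defined in Section 7.4) will be captured as an efficacy measure and in general will not be" so recorded. The same paragraph asks sites to record as adverse events any new pulmonary symptoms that fall short of the pneumonia definition. It also keeps a route for serious cases: "Events that meet the criteria for an SAE (Section 9.2) should follow the procedures for SAE reporting as detailed in Section 9.3".

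Protocol 7.1 uses the same cross-reference for the primary endpoint but adds two limits. The event must be *S. aureus* "pneumonia as defined in Section 7.4 up to but not including Day 22". Protocol 7.3 lists non-*S. aureus* pneumonia as an exploratory efficacy endpoint, again with a window: "pneumonias up to but not including Day 22 in the MITT, ITT, and PP Populations".

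SAP 7.13.1 builds the TEAE tables (by preferred term, severity and relationship) from reported adverse events. It has no rule for bringing in pneumonias recorded only as efficacy events.

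**The concern.** The product neutralises *S. aureus* toxins. A pneumonia caused by another organism is not a failure of that action; in a placebo-controlled trial it is an ordinary safety outcome and should be compared between arms as one. If 9.1 removes it from adverse events, the TEAE tables under-count a respiratory infection that matters in ventilated patients, and no severity or relatedness is recorded for the exempt cases.

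The rule also runs the wrong way round. Pulmonary symptoms that do not amount to pneumonia must be recorded, while the full pneumonia generally need not be. The words that make the exemption general rather than absolute leave the choice to each of about 70 sites, so the same event may be recorded at one site and not at another.

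**Working it through.** The point rests on no stated figure, so the check sets the sections side by side.

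**1. Which pneumonia does 9.1 exempt?** Section 7.4 holds two definitions.
- Section 7.4.1 defines *S. aureus* pneumonia. It needs a positive culture from an adequate specimen, with clinical signs within 2 days either side.
- Table 2 defines HABP and VABP by chest imaging, exposure, pulmonary signs and systemic signs. It has no culture criterion.

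Section 9.1 speaks of pneumonia without an organism, and Section 7.4.2 sends an unqualified diagnosis of pneumonia to Table 2. Section 7.1 adds the organism where it is meant; 9.1 does not. The plain reading is therefore Table 2, which includes Gram-negative pneumonia.

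**2. Until when?** The text can be read both ways.
- *For a limit at about Day 22:* 7.4.1 and the daily assessments in 7.4.2 are framed by the Monitoring Period, which Section 9.7 gives as Day 2 through Day 22. Appendix A schedules no pneumonia sign or symptom assessment at the Day 28, Day 40 to 89 or Day 90 visits.
- *Against:* 7.1 adds the Day 22 limit separately, which suggests that 7.4 carries none. Table 2 HABP extends to signs starting within 7 days after hospital discharge. Adverse events "will be monitored and documented until study participation is complete".

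The result is ambiguity, not a stated exemption to Day 90.

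**3. Where does each kind of event appear?**

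| Event | Before Day 22 | From Day 22 |
|---|---|---|
| Serious, any organism | SAE reporting and tables | SAE reporting to Day 90, and tables |
| *S. aureus*, non-serious | Primary and additional analyses (SAP 7.11.1, 7.11.2) | Kaplan-Meier analyses by Day 90, Investigator's judgement (SAP 7.11.2) |
| Non-*S. aureus*, non-serious | Exploratory incidence (SAP 7.11.4), by randomized arm, no severity or causality; in TEAE tables only if the site records it | No incidence endpoint; in TEAE tables only if the site records it |

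The last row is the gap.

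**4. A qualification on the last cell.** Protocol 7.3 and SAP 5.2.6 state no window for the incidence of all bacterial pneumonias; SAP 7.11.4 closes it before Day 22. The table follows SAP 7.11.4, the analysis section. An open window would help little, because after Day 22 the only scheduled assessment likely to pick up such a case is the adverse-event assessment, which is the one 9.1 puts in doubt.

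**5. Size.** The number missing is N × r × s, where N = 354 is the planned number randomized, r is the share of subjects with a non-*S. aureus* pneumonia (one each), and s is the share of those that are non-serious and unrecorded. The documents give neither r nor s. Assuming r from 5% to 20% and s from 10% to 50%, the result runs from 354 × 0.05 × 0.10 = 1.8 to 354 × 0.20 × 0.50 = 35.4. That twentyfold range comes wholly from the assumptions, so it is not an estimate.

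**The case against.** The strongest defence is that the exemption is for lack of efficacy and covers events that will be captured as an efficacy measure. A Gram-negative pneumonia on Day 30 is neither, so the default of recording all adverse events should apply. Serious cases are kept in any event. The criteria in 9.2 include "Requires hospitalization or prolongation of existing hospitalizations", which many pneumonias in this population may meet, and under 9.3 "all SAEs occurring from the time of randomization until the Day 90 Safety Visit, must be reported to Medpace Clinical Safety within 24 hours". Before Day 22 the ITT tables count non-*S. aureus* pneumonia in every randomized subject, so an imbalance would be visible. Protocol 1.3 does not name replacement infection as a risk.

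Much of this stands, and it limits the point. It does not remove it. The defence needs an investigator to set aside the cross-reference to Section 7.4, and the protocol does not say to do so. Whether pneumonia prolongs the stay of a patient already in intensive care is a judgement. Section 9.2 also defines seriousness for adverse events and reactions, a class that 9.1 has just said pneumonia generally falls outside. The exploratory tables show incidence by randomized arm, without severity or causality.

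A reader might go further and infer three things that the documents do not support:
- *That every pneumonia to Day 90 is exempt.* The missing end date is silence, and the Monitoring Period framing points the other way.
- *That exempt pneumonias reach no planned summary.* SAP 7.11.4 counts them before Day 22, and also summarizes pneumonia-free days and Day 28 mortality for subjects with any pneumonia.
- *That nothing about pneumonia is analysed after Day 21.* SAP 7.11.2 analyses *S. aureus* pneumonia by Day 90.

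**Conclusion.** The concern holds for one class of event: non-serious, non-*S. aureus* pneumonia. Under the plain reading of 9.1 it may be absent from the TEAE tables throughout follow-up. From Day 22 it is also outside every planned incidence endpoint, taking SAP 7.11.4 as governing. Events may drop out rather than must, because the rule leaves discretion and its duration is unclear; uneven handling between sites is part of the defect.

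The conclusion assumes that 9.1 points to Table 2 and that sites apply it as written. The number of events cannot be stated from the documents. The primary efficacy analysis is not affected. The point is worth correcting because the wording gives a poorer safety record for no gain.

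**What to change.** In Protocol 9.1, limit the exemption to *S. aureus* pneumonia as defined in Section 7.4 with onset before Day 22, which is the primary-endpoint event. State that every other pneumonia through Day 90 (another organism at any time, or any organism with onset from Day 22) is recorded as an adverse event with severity and causality. Leave the SAE sentence as it is.

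In SAP 7.13.1, add one Safety Population table, by actual treatment, of all pneumonias to Day 90, whether they were captured as efficacy events, adverse events or SAEs, with each event counted once. For pneumonias that remain exempt and non-serious the table can give incidence only.

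When making the change, align the wording with SAP 5.2.1, where pneumonia is diagnosed on the Investigator's judgement and the HABP/VABP definitions serve only to categorize it. Otherwise 9.1 and the SAP would refer to different sets of events.

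The cost is a short protocol change or a site clarification, plus one table. Some pneumonias before Day 22 would be entered on two eCRF pages.
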